## **7.4 SOURCE DATA DOCUMENTATION**

Study monitors will perform ongoing source data verification and review to confirm that critical protocol data (i.e., source data) entered into the eCRFs by authorized site personnel are accurate, complete, and verifiable from source documents.

Source documents (paper or electronic) are those in which patient data are recorded and documented for the first time. They include, but are not limited to, hospital records, clinical and office charts, laboratory notes, memoranda, patient-reported outcomes, evaluation checklists, pharmacy dispensing records, recorded data from automated instruments, copies of transcriptions that are certified after verification as being accurate and complete, microfiche, photographic negatives, microfilm or magnetic media, X-rays, patient files, and records kept at pharmacies, laboratories, and medico-technical departments involved in a clinical trial.

Before study initiation, the types of source documents that are to be generated will be clearly defined in the Trial Monitoring Plan. This includes any protocol data to be entered directly into the eCRFs (i.e., no prior written or electronic record of the data) and considered source data.

Source documents that are required to verify the validity and completeness of data entered into the eCRFs must not be obliterated or destroyed and must be retained per the policy for retention of records described in Section 7.6.

To facilitate source data verification and review, the investigators and institutions must provide the Sponsor direct access to applicable source documents and reports for trial-related monitoring, Sponsor audits, and IRB/EC review. The study site must also allow inspection by applicable health authorities.

## **7.5 USE OF COMPUTERIZED SYSTEMS**

When clinical observations are entered directly into a study site's computerized medical record system (i.e., in lieu of original hardcopy records), the electronic record can serve as the source document if the system has been validated in accordance with health authority requirements pertaining to computerized systems used in clinical research. An acceptable computerized data collection system allows preservation of the original entry of data. If original data are modified, the system should maintain a viewable audit trail that shows the original data as well as the reason for the change, name of the person making the change, and date of the change.

## **7.6 RETENTION OF RECORDS**

Records and documents pertaining to the conduct of this study and the distribution of IMP, including eCRFs, electronic or paper PRO and ClinRO data (if applicable), Informed Consent Forms, laboratory test results, medication inventory records, and images, must be retained by the investigator for 15 years after completion or

discontinuation of the study or for the length of time required by relevant national or local health authorities, whichever is longer. After that period of time, the documents may be destroyed, subject to local regulations.

No records may be disposed of without the written approval of the Sponsor. Written notification should be provided to the Sponsor prior to transferring any records to another party or moving them to another location.

The Sponsor will retain study data for 25 years after the final study results have been reported or for the length of time required by relevant national or local health authorities, whichever is longer.

## **8. ETHICAL CONSIDERATIONS**

### **8.1 COMPLIANCE WITH LAWS AND REGULATIONS**

This study will be conducted in full conformance with the ICH E6 guideline for Good Clinical Practice and the principles of the Declaration of Helsinki, or the applicable laws and regulations of the country in which the research is conducted, whichever affords the greater protection to the individual. The study will comply with the requirements of the ICH E2A guideline (Clinical Safety Data Management: Definitions and Standards for Expedited Reporting). Studies conducted in the United States or under a U.S. Investigational New Drug (IND) Application will comply with U.S. FDA regulations and applicable local, state, and federal laws. Studies conducted in the European Union or European Economic Area will comply with the E.U. Clinical Trials Directive (2001/20/EC) or Clinical Trials Regulation (536/2014) and applicable local, regional, and national laws.

### **8.2 INFORMED CONSENT**

The Sponsor's sample Informed Consent Form (and ancillary sample Informed Consent Forms such as an Assent Form or Mobile Nursing Informed Consent Form, if applicable) will be provided to each site. If applicable, it will be provided in a certified translation of the local language. The Sponsor or its designee must review and approve any proposed deviations from the Sponsor's sample Informed Consent Forms or any alternate consent forms proposed by the site (collectively, the "Consent Forms") before IRB/EC submission. The final IRB/EC-approved Consent Forms must be provided to the Sponsor for health authority submission purposes according to local requirements.

If applicable, the Informed Consent Form will contain separate sections for any optional procedures. The investigator or authorized designee will explain to each patient the objectives, methods, and potential risks associated with each optional procedure. Patients will be told that they are free to refuse to participate and may withdraw their consent at any time for any reason. A separate, specific signature will be required to document a patient's agreement to participate in optional procedures. Patients who decline to participate will not provide a separate signature.

The Consent Forms must be signed and dated by the patient or the patient's legally authorized representative before his or her participation in the study. The case history or clinical records for each patient shall document the informed consent process and that written informed consent was obtained prior to participation in the study.

The Consent Forms should be revised whenever there are changes to study procedures or when new information becomes available that may affect the willingness of the patient to participate. The final revised IRB/EC-approved Consent Forms must be provided to the Sponsor for health authority submission purposes.

If the Consent Forms are revised (through an amendment or an addendum) to communicate information that might affect a patient's willingness to continue in the study, the patient or a legally authorized representative must re-consent by signing the most current version of the Consent Forms or the addendum, in accordance with applicable laws and IRB/EC policy. For any updated or revised Consent Forms, the case history or clinical records for each patient shall document the informed consent process and that written informed consent was obtained using the updated/revised Consent Forms for continued participation in the study.

A copy of each signed Consent Form must be provided to the patient or the patient's legally authorized representative. All signed and dated Consent Forms must remain in each patient's study file or in the site file and must be available for verification by study monitors at any time.

For sites in the United States, each Consent Form may also include patient authorization to allow use and disclosure of personal health information in compliance with the U.S. Health Insurance Portability and Accountability Act (HIPAA) of 1996. If the site utilizes a separate Authorization Form for patient authorization for use and disclosure of personal health information under the HIPAA regulations, the review, approval, and other processes outlined above apply except that IRB review and approval may not be required per study site policies.

### **8.3 INSTITUTIONAL REVIEW BOARD OR ETHICS COMMITTEE**

This protocol, the Informed Consent Forms, any information to be given to the patient, and relevant supporting information must be submitted to the IRB/EC by the investigator and reviewed and approved by the IRB/EC before the study is initiated. In addition, any patient recruitment materials must be approved by the IRB/EC.

The investigator is responsible for providing written summaries of the status of the study to the IRB/EC annually or more frequently in accordance with the requirements, policies, and procedures established by the IRB/EC. Investigators are also responsible for promptly informing the IRB/EC of any protocol amendments (see Section 9.6).

In addition to the requirements for reporting all adverse events to the Sponsor, investigators must comply with requirements for reporting serious adverse events to the local health authority and IRB/EC. Investigators may receive written IND safety reports or other safety-related communications from the Sponsor. Investigators are responsible for ensuring that such reports are reviewed and processed in accordance with health authority requirements and the policies and procedures established by their IRB/EC, and archived in the site's study file.

## **8.4 CONFIDENTIALITY**

Information technology systems used to collect, process, and store study-related data are secured by technical and organizational security measures designed to protect such data against accidental or unlawful loss, alteration, or unauthorized disclosure or access. In the event of a data security breach, appropriate mitigation measures will be implemented.

The Sponsor maintains confidentiality standards by coding each patient enrolled in the study through assignment of a unique patient identification number. This means that patient names are not included in data sets that are transmitted to any Sponsor location.

Patient medical information obtained by this study is confidential and may be disclosed to third parties only as permitted by the Informed Consent Form (or separate authorization for use and disclosure of personal health information) signed by the patient, unless permitted or required by law.

Medical information may be given to a patient's personal physician or other appropriate medical personnel responsible for the patient's welfare, for treatment purposes.

Given the complexity and exploratory nature of exploratory biomarker analyses, data derived from these analyses will generally not be provided to study investigators or patients unless required by law. The aggregate results of any conducted research will be available in accordance with the effective Sponsor policy on study data publication (see Section 9.6).

Data generated by this study must be available for inspection upon request by representatives of national and local health authorities, Sponsor monitors, representatives, and collaborators, and the IRB/EC for each study site, as appropriate.

Study data, which may include imaging data and data on genomic variants, may be submitted to government or other health research databases or shared with researchers, government agencies, companies, or other groups that are not participating in this study. These data may be combined with or linked to other data and used for research purposes, to advance science and public health, or for analysis, development, and commercialization of products to treat and diagnose disease. In addition, data may be disseminated as described in Section 9.6.

## **8.5 FINANCIAL DISCLOSURE**

Investigators will provide the Sponsor with sufficient, accurate financial information in accordance with local regulations to allow the Sponsor to submit complete and accurate financial certification or disclosure statements to the appropriate health authorities. Investigators are responsible for providing information on financial interests during the course of the study and for 1 year after completion of the study (see definition of end of study in Section 3.2).

## **9. STUDY DOCUMENTATION, MONITORING, AND ADMINISTRATION**

### **9.1 STUDY DOCUMENTATION**

The investigator must maintain adequate and accurate records to enable the conduct of the study to be fully documented, including, but not limited to, the protocol, protocol amendments, Informed Consent Forms, and documentation of IRB/EC and governmental approval. In addition, at the end of the study, the investigator will receive the patient data, including an audit trail containing a complete record of all changes to data.

### **9.2 PROTOCOL DEVIATIONS**

The investigator should document and explain any protocol deviations. The investigator should promptly report any deviations that might have an impact on patient safety and data integrity to the Sponsor and to the IRB/EC in accordance with established IRB/EC policies and procedures. The Sponsor will review all protocol deviations and assess whether any represent a serious breach of Good Clinical Practice guidelines and require reporting to health authorities. As per the Sponsor's standard operating procedures, prospective requests to deviate from the protocol, including requests to waive protocol eligibility criteria, are not allowed.

### **9.3 MANAGEMENT OF STUDY QUALITY**

The Sponsor will implement a risk-based quality management approach to ensure the quality of the study, focusing on processes and data that are critical to ensuring patient safety and data integrity. Prior to study initiation, the Sponsor will identify and evaluate potential risks associated with critical study processes and data, and will implement appropriate mitigation plans for evaluating and controlling these risks. Details regarding the applied approach for the study will be provided in an Integrated Quality Risk Strategy.

Risk control will include the selection of risk-based parameters and an evaluation for quality tolerance limits (QTLs). For studies applying QTLs, details on the management and review of QTLs will be provided in a separate Quality Tolerance Limit Plan.

## **9.4 SITE INSPECTIONS**

Site visits will be conducted by the Sponsor or an authorized representative for inspection of study data, patients' medical records, and eCRFs. The investigator will permit national and local health authorities; Sponsor monitors, representatives, and collaborators; and the IRBs/ECs to inspect facilities and records relevant to this study.

## **9.5 ADMINISTRATIVE STRUCTURE**

This trial will be sponsored and managed by Genentech, Inc. The Sponsor will provide clinical operations management, data management, and medical monitoring.

Approximately [REDACTED] will participate to enroll approximately 210 patients. Enrollment will occur through an IxRS.

Central facilities will be used for certain study assessments throughout the study (e.g., specified laboratory tests, biomarker and PK analyses), as specified in Section 4.5. Accredited local laboratories will be used for routine monitoring; local laboratory ranges will be collected.

## **9.6 DISSEMINATION OF DATA AND PROTECTION OF TRADE SECRETS**

Regardless of the outcome of a trial, the Sponsor is dedicated to openly providing information on the trial to health care professionals and to the public, at scientific congresses, in clinical trial registries, and in peer-reviewed journals. The Sponsor will comply with all requirements for publication of study results. Study data may be shared with others who are not participating in this study (see Section 8.4 for details), and redacted Clinical Study Reports and/or other summaries of clinical study results may be available in health authority databases for public access, as required by local regulation, and will be made available upon request. For more information, refer to the Roche Global Policy on Sharing of Clinical Study Information at the following website:

<https://www.roche.com/innovation/process/clinical-trials/data-sharing/>

The results of this study may be published or presented at scientific congresses. For all clinical trials in patients involving an IMP for which a marketing authorization application has been filed or approved in any country, the Sponsor aims to submit a journal manuscript reporting primary clinical trial results within 6 months after the availability of the respective Clinical Study Report. In addition, for all clinical trials in patients involving an IMP for which a marketing authorization application has been filed or approved in any country, the Sponsor aims to publish results from analyses of additional endpoints and exploratory data that are clinically meaningful and statistically sound.

The investigator must agree to submit all manuscripts or abstracts to the Sponsor prior to submission for publication or presentation. This allows the Sponsor to protect

proprietary information and to provide comments based on information from other studies that may not yet be available to the investigator.

In accordance with standard editorial and ethical practice, the Sponsor will generally support publication of multicenter trials only in their entirety and not as individual center data. In this case, a coordinating investigator will be designated by mutual agreement.

Authorship will be determined by mutual agreement and in line with International Committee of Medical Journal Editors authorship requirements. Any formal publication of the study in which contribution of Sponsor personnel exceeded that of conventional monitoring will be considered as a joint publication by the investigator and the appropriate Sponsor personnel.

Any inventions and resulting patents, improvements, and/or know-how originating from the use of data from this study will become and remain the exclusive and unburdened property of the Sponsor, except where agreed otherwise.

## **9.7                    PROTOCOL AMENDMENTS**

Any protocol amendments will be prepared by the Sponsor. Protocol amendments will be submitted to the IRB/EC and to regulatory authorities in accordance with local regulatory requirements.

Approval must be obtained from the IRB/EC and regulatory authorities (as locally required) before implementation of any changes, except for changes necessary to eliminate an immediate hazard to patients or changes that involve logistical or administrative aspects only (e.g., change in Medical Monitor or contact information).

## **Appendix 1**

### **Schedule of Activities: Induction**

## Appendix 1: Schedule of Activities for Induction

---

ADA=anti-drug antibody; ATE=active treatment extension; CMV=cytomegalovirus; CRP=C-reactive protein; FeCal=fecal calprotectin; IxRS=interactive voice or web-based response system; PK=pharmacokinetic; PRO=patient-reported outcome; [REDACTED] TB=tuberculosis; TD=treatment discontinuation; UC-PRO/SS=Ulcerative Colitis Patient-Reported Outcomes Signs and Symptoms; UV=unscheduled visit; WES=whole exome sequencing; WGS=whole genome sequencing.

**Notes: On treatment days, all assessments should be performed prior to study treatment administration, unless otherwise specified.**

*Assessments shaded in gray are not applicable for sites in China.*

## Appendix 1: Schedule of Activities for Induction

---

[figure not shown]
- a Results of standard-of-care assessments performed prior to obtaining informed consent and within 35 days prior to Day 1 may be used; such assessments do not need to be repeated for screening. Patients who do not meet the criteria for participation in this study may qualify for one re-screening opportunity (for a total of two screenings per patient) at the investigator's discretion, as described in Section 3.1.1.
- b Patients may continue to the optional ATE period (Appendix 2) following completion of the [REDACTED] visit. For patients who do not continue to the optional ATE period, the [REDACTED] visit will also serve as the treatment completion visit; these patients will then enter the safety follow-up period.
- c Patients who discontinue study treatment prematurely during the induction period will return to the clinic for a treatment discontinuation visit within 14 days after their final dose of study treatment and will then enter the safety follow-up period.
- d Patients will undergo follow-up assessments at [REDACTED] after their final dose of study treatment.
- e Unscheduled visits may be performed if clinically indicated (e.g., for evaluation of an adverse event). The specified assessments are required at each unscheduled visit. Assessments listed in parentheses are not required, but may be performed for patients who receive rescue therapy or experience persistent or worsening disease for which rescue therapy is indicated, as determined by the investigator. Additional assessments may be performed if clinically indicated, as determined by the investigator.
- f Informed consent must be documented before any study-specific screening procedure is performed and may be obtained more than 35 days before initiation of study treatment.
- g Stool samples should be obtained prior to bowel preparation for endoscopy (colonoscopy or sigmoidoscopy), if applicable.
- h Samples will be analyzed for culture and sensitivity, ova and parasites, and *C. difficile*.
- i Patients assigned to the vixarelimab [REDACTED] arm will receive [REDACTED] vixarelimab at [REDACTED]. Patients assigned to the vixarelimab [REDACTED] arm will receive [REDACTED] vixarelimab at [REDACTED] to maintain blind, these patients will also receive [REDACTED]. Patients assigned to placebo [REDACTED] will receive placebo at [REDACTED].
- j Study treatment should not be administered at the [REDACTED] visit if the patient elects not to continue to the optional ATE period.
- k Record medications used by a patient from the start of the screening period to initiation of study treatment.
- l After informed consent has been obtained but prior to initiation of study treatment, only serious adverse events caused by a protocol-mandated intervention should be reported. After initiation of study treatment, all adverse events will be reported until [REDACTED] after the final dose of study treatment. After this period, the Sponsor should be notified if the investigator becomes aware of any serious adverse event that is believed to be related to prior exposure to study treatment (see Section 5.6).
- m Includes evaluation of the head, eyes, ears, nose, and throat, and the cardiovascular, dermatologic, musculoskeletal, respiratory, gastrointestinal, genitourinary, and neurologic systems.
- n Perform a limited, symptom-directed examination at specified timepoints or as clinically indicated.
- o ECG recordings should be performed prior to *invasive* procedures scheduled at that same time (e.g., blood draws). *Vital sign measurements, physical examinations, and diary training may be conducted prior to performing the ECG.* See Section 4.5.5.

## Appendix 1: Schedule of Activities for Induction

---

[figure not shown]
- p All women of childbearing potential will have a serum pregnancy test performed at screening. Urine pregnancy tests will be performed at specified subsequent visits during treatment, at the treatment discontinuation visit, and at [REDACTED] after the final dose of study treatment. Urine pregnancy tests will be reviewed prior to each study drug administration for confirmation of a negative result. If a urine pregnancy test is positive, it must be confirmed by a serum pregnancy test.
- q All patients will undergo either a colonoscopy or a flexible sigmoidoscopy at specified timepoints. Patients without documentation of a colonoscopy within 2 years prior to screening must undergo a colonoscopy in lieu of a flexible sigmoidoscopy at screening. The screening endoscopy will be used as efficacy baseline and for inclusion. Video recordings should be taken of the entire endoscopic procedure (colonoscopy or flexible sigmoidoscopy), starting from insertion into the bowel. Biopsies should be performed upon withdrawal of the endoscope from the bowel. Technical instructions for video recording and biopsy collection will be provided in the endoscopy and/or laboratory manual.
- r Tissue collected at screening will be analyzed for CMV, *if required (see Section 4.1.2)*, as determined by histologic examination or immunohistochemistry per local standards, and will undergo histopathologic examination for patients without a prior histopathology report. Tissue collected at screening and subsequent timepoints will also be used for histologic assessments and exploratory biomarker research *at participating sites, excluding China (see Appendix 9)*. *For endoscopy assessments after screening for sites located in China, endoscopy will be performed but no biopsy will be collected.*
- s See [Appendix 3](#). *The Mayo Score will be calculated by the Sponsor.*
- t Clinician-reported outcome instruments will be completed after the physical examination, prior to the administration of study treatment.
- u An electronic diary will be used to collect PRO data, including stool frequency/rectal bleeding and the UC-PRO/SS instrument (see Section 4.5.7.2). Stool frequency and rectal bleeding will be recorded daily; UC-PRO/SS will be collected daily during screening and daily over at least a 7-day period before each specified study visit.
- v On treatment days, all samples should be collected prior to dosing.
- w Additional ADA samples should be collected in patients with signs and symptoms of injection-related reactions.
- x Not applicable for a site that has not been granted approval for WGS/WES. If a sample is not collected at the randomization visit (Day 1), it may be collected at any subsequent visit.

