
 
• To evaluate the immune response to vixarelimab
 
	
 
• Prevalence of ADAs at baseline and incidence of ADAs during the study
 

ADA=anti-drug antibody; DAIDS=Division of AIDS; mMS=modified Mayo Score.

a Modified Mayo Score is the composite of three Mayo Score assessments: stool frequency, rectal bleeding, and centrally read endoscopy (see [Appendix 3](#)).

b Endoscopy scores will be based on interpretation by a blinded central reader.

c Adverse events will be graded according to the DAIDS Table for Grading the Severity of Adult and Pediatric Adverse Events (HHS 2017), with slight modifications for clarity and for alignment with internal practices (see [Section 5.3.3](#) and [Appendix 7](#)).

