**Table 1 Objectives and Corresponding Endpoints (cont.)**

Exploratory Objectives	Corresponding Endpoints

 
To evaluate the long-term efficacy of vixarelimab
 
	
 
Sustained remission, defined as clinical remission at [REDACTED] Week 12 [REDACTED]
 
Clinical remission at [REDACTED]
 
Clinical response at [REDACTED]
 
Endoscopic improvement at [REDACTED]
 
Endoscopic remission at [REDACTED]
 
Change from baseline in UC bowel movement signs and symptoms at Week 12 and [REDACTED], as assessed by UC-PRO/SS score
 
Improvement in UC bowel movement signs and symptoms at Week 12 [REDACTED], as defined by the proportion of patients with a <math>\geq 6</math>-point decrease in the UC-PRO/SS bowel domain score
 
Change from baseline in UC functional signs and symptoms at Week 12 and [REDACTED], as assessed by UC-PRO/SS score
 
Improvement in UC functional symptoms at Week 12 and [REDACTED], as defined by the proportion of patients with a <math>\geq 2</math>-point decrease in the UC-PRO/SS functional domain score
 

 
To evaluate potential relationships between vixarelimab exposure and the efficacy and safety of vixarelimab
 
	
 
Relationship between PK parameters for vixarelimab and efficacy endpoints
 
Relationship between PK parameters for vixarelimab and safety endpoints
 

 
To evaluate potential relationships between selected covariates and exposure to vixarelimab
 
	
 
Relationship between selected covariates and PK parameters for vixarelimab
 

 
To evaluate potential effects of ADAs
 
	
 
Relationship between ADA status and efficacy, safety, or PK endpoints
 

ADA=anti-drug antibody; PK=pharmacokinetic; UC=ulcerative colitis; UC-PRO/SS=Ulcerative Colitis Patient-Reported Outcomes Signs and Symptoms.

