## **6.7 IMMUNOGENICITY ANALYSES**

The immunogenicity analysis population will consist of all patients with at least one postdose ADA assessment. Patients will be grouped according to treatment received or, if no treatment is received prior to study discontinuation, according to treatment assigned.

The numbers and proportions of ADA-positive patients and ADA-negative patients at baseline (baseline prevalence) and after drug administration (postbaseline incidence) will be summarized by treatment group. When determining postbaseline incidence, patients are considered to be ADA positive if they are ADA negative or have missing data at baseline but develop an ADA response following study drug exposure (treatment-induced ADA response), or if they are ADA positive at baseline and the titer of one or more postbaseline samples is at least 0.60 titer unit greater than the titer of the baseline sample (treatment-enhanced ADA response). Patients are considered to be ADA negative if they are ADA negative or have missing data at baseline and all postbaseline samples are negative, or if they are ADA positive at baseline but do not

[figure not shown]
have any postbaseline samples with a titer that is at least 0.60 titer unit greater than the titer of the baseline sample (treatment unaffected).

The relationship between ADA status and safety, efficacy, PK, and biomarker endpoints may be analyzed and reported via descriptive statistics.

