#### **PROCEDURES**

In the event of a suspected anaphylactic reaction during study treatment administration, the following procedures should be performed:

- Stop the study treatment administration, if possible.
- Call for additional medical assistance.
- Maintain an adequate airway.
- Ensure that appropriate monitoring is in place, with continuous ECG and pulse oximetry monitoring if possible.
- Administer antihistamines, epinephrine, or other medications and IV fluids as required by patient status and as directed by the physician in charge.
- Continue to observe the patient and document observations.
- Collect serum samples for immunogenicity testing.
- Ask the patient to return for immunogenicity sample collection at the time of washout, if appropriate.

## Appendix 6

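### ADA status counts any positive postbaseline sample, and extra samples are drawn only after reactions, so the ADA versus injection-reaction comparison can be biased away from the null

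*Combined protocol and SAP*

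**What the plan says.** **Sampling.** Footnote w of Appendix 1 (induction) and footnote s of Appendix 2 (extension) both state "Additional ADA samples should be collected in patients with signs and symptoms of injection-related reactions". Neither gives a number or a time for these samples. The procedures in Appendix 5 call for immunogenicity serum after a suspected anaphylactic reaction and then: "Ask the patient to return for immunogenicity sample collection at the time of washout, if appropriate".

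**Classification (Section 6.7).** A patient who does not start ADA positive is negative only if "ADA negative or have missing data at baseline and all postbaseline samples are negative". A patient who starts positive counts as treatment-enhanced if "the titer of one or more postbaseline samples is at least 0.60 titer unit greater than the titer of the baseline sample". Both rules run over every postbaseline sample. Neither separates scheduled from event-triggered samples.

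**Use.** Table 1 lists "Prevalence of ADAs at baseline and incidence of ADAs during the study" as a secondary endpoint and "Relationship between ADA status and efficacy, safety, or PK endpoints" as an exploratory one. For the latter, Section 6.7 says: "The relationship between ADA status and safety, efficacy, PK, and biomarker endpoints may be analyzed and reported via descriptive statistics". Further detail is deferred to a Data Analysis Plan (DAP) that is not among the documents.

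**The concern.** How often ADA status is tested depends on the outcome with which it will be compared. Under an any-positive rule an added sample can raise a patient's chance of being called positive and can never lower it. The added samples go only to patients who reacted.

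This matters because hypersensitivity is the potential risk named in Section 5.1.1, and its more severe forms are adverse events of special interest in Section 5.2.3. The benefit–risk text in Section 1.3 relies on earlier studies showing no evident link between ADA and safety. A sampling artefact could appear to contradict that, or could make a real signal hard to read. Section 4.2.2 says postbaseline placebo samples are not assayed unless requested, so the trial has no routine internal estimate of how often the assay is positive in patients not given the drug.

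**Working it through.** The plan states no expected ADA incidence, reaction rate, sample count or assay false-positive rate, so there is no figure to reproduce. The inputs below are assumptions, varied over a range.

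**Inputs**
- K, scheduled postdose ADA samples: 3, 5 or 7 (the schedule tables are not available)
- m, extra samples in a patient who reacts: 1, 2 or 3 (the footnotes give no number)
- q, chance that one sample is falsely or transiently positive: 1%, 2% or 5%, independent between samples
- r, proportion of patients who react: 5%, 10% or 20%
- No true link between ADA and reactions

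**Step 1: spurious odds ratio.** P(positive) = 1 − (1 − q)^n, with n = K for non-reactors and n = K + m for reactors.

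At K = 5 and q = 2%, non-reactors have 1 − 0.98^5 = 9.6%. Reactors have:

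| Extra samples | P(positive) | Odds ratio |
|---|---|---|
| 1 | 1 − 0.98^6 = 11.4% | 1.21 |
| 2 | 1 − 0.98^7 = 13.2% | 1.43 |
| 3 | 1 − 0.98^8 = 14.9% | 1.65 |

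Over the whole grid the odds ratio runs from 1.15 (K = 7, m = 1, q = 1%: 6.8% versus 7.7%) to 2.17 (K = 3, m = 3, q = 5%: 14.3% versus 26.5%). With K samples in both groups it is 1.00.

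**Step 2: the case with practically no bias.** Suppose a fraction π of patients (5% or 10%) have persistent ADA, each sample detects it with sensitivity s (80–100%), and each sample in the other patients is falsely positive with probability f. Then P(n) = π[1 − (1 − s)^n] + (1 − π)[1 − (1 − f)^n]. Take K = 3 or 5 and one extra sample.
- f = 0: odds ratio 1.00 to 1.01. Example: π = 5%, s = 80%, K = 3 gives 4.96% versus 4.99%.
- f = 1%: odds ratio 1.07 to 1.13. The same example gives 7.78% versus 8.74%, odds ratio 1.13.

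**Step 3: the 0.60-titer rule.** Baseline-positive patients with no true change were simulated, with normal titer error of the same SD at baseline and afterwards (SD assumed). Going from three to four postbaseline samples raises the proportion called treatment-enhanced from 4.3% to 5.4% at SD 0.2, and from 17.6% to 21.1% at SD 0.3.

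**Step 4: overall incidence.** Only reactors contribute, so the added incidence is r × [P(K + m) − P(K)].
- K = 5, q = 2%, r = 10%: 0.10 × (11.4% − 9.6%) = 0.18 point with one extra sample, and 0.53 point with three.
- Over all 81 combinations the range is 0.05 to 2.45 points, and 70 of the 81 stay below 1 point.
- In patients: if allocation is 1:1:1 (the ratio is redacted), 210 × 2/3 = 140 receive active drug and 14 react. The rule then adds about 0.25 ADA-positive patients with one extra sample and about 0.5 with two.

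**The case against.** **The bias is conditional.** A reader might infer that the association is inflated as a matter of fact. The documents do not support that. They give no assay specificity and no information on ADA persistence, and Section 1.3 says only that ADA rates have generally been low. Step 2 shows practically no bias when ADA persist and the assay is specific. This stands.

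**Extra samples may not be independent chances.** Section 5.3.5.1 deals with reactions during dosing or in the following 24 hours, and samples on treatment days are taken before the dose. A sample drawn at the reaction may nearly duplicate the scheduled one. The independence in Step 1 is then too strong and its odds ratios too large.

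**Severe reactors may lose scheduled samples.** Table 3 and Section 4.6.1 require permanent discontinuation after Grade 4 reactions and after confirmed, related anaphylaxis. As an illustration at q = 3%, two scheduled plus one extra sample gives 1 − 0.97^3 = 8.7%, against 1 − 0.97^4 = 11.5% for four scheduled samples: odds ratio 0.74, the opposite direction. This concerns only the most severe reactors, and their discontinuation or follow-up visits may include ADA samples. It shows that the net direction is not certain in that group.

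**Scheduled-only status has its own error.** It drops the samples closest to the reaction. A patient with a true ADA-mediated reaction who stops early could be called negative or have no evaluable sample. Also, a real but transient ADA found by an extra sample is better ascertainment, not a false result. This stands, and it argues against making scheduled-only status the sole rule.

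**The analysis is minor by design, and the DAP may settle the matter.** The relationship is exploratory, optional and descriptive. The DAP may contain a rule for unscheduled samples. However, Section 6.7 already defines the classification down to the titer threshold and, as written, it includes every postbaseline sample.

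**Conclusion.** The point holds in a limited form. The text makes ascertainment of ADA status depend on the reaction with which it is compared, and the documents contain no safeguard. The comparison of ADA status with injection or hypersensitivity reactions can therefore be biased away from the null when positives are transient or false. The illustrative odds ratio is 1.15 to 2.17 under the Step 1 assumptions, 1.07 to 1.13 with persistent ADA plus 1% false positivity, and about 1.00 with persistent ADA and a specific assay. The documents do not say which case applies.

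Three stronger readings are tempting and not supported:
- **That the secondary endpoint, ADA incidence, is materially inflated.** The effect is confined to reactors and is usually below 1 percentage point.
- **That incidence cannot be compared between the two regimens.** This needs different reaction rates, and none are given. At K = 5, q = 2% and one extra sample, a 10-point gap in reaction rate moves incidence by about 0.18 point.
- **That every ADA–safety association is affected.** The extra sampling is tied to injection and hypersensitivity reactions, so the differential bias bears directly on those only.

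No hypothesis test, error rate or primary conclusion depends on this analysis.

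**What to change.** In Section 6.7 and the DAP:
- For the comparison of ADA status with injection or hypersensitivity reactions, derive ADA status from protocol-scheduled samples and present it beside the status from all samples.
- Report ADA incidence from all samples, with a scheduled-only sensitivity summary.
- Flag event-triggered samples (Appendix 1 footnote w, Appendix 2 footnote s, Appendix 5) in the data and list them for individual case review.

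Sample collection does not change and no result is discarded. The cost is a few sentences, a flag and one extra summary. Scheduled-only status may miss ADA in patients who react and stop early, which is why both versions should be shown. If the DAP already has such a rule, a cross-reference in Section 6.7 is enough.
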